9. RESEARCH METHODS

9.1. Study design

This is a retrospective, observational study using January 1, 2006 – December 31, 2023 data from the National VA Health Care Network databases. PC patients who initiated relugolix will be selected based on diagnosis codes, age, treatment received, and continuous activity in the health care network. The identification period for relugolix use will be from December 18, 2020 to December 31, 2023. December 18, 2020 is the approval date for relugolix in the US, and December 31, 2023 is the end of available data. The index date will be defined as the initiation date of relugolix. The baseline period will be 365 days prior to the index date (hence the start of the study period is December 18, 2019). The follow-up period will be from the index date to the earliest of death, end of continuous eligibility or end of data availability. Most of the patient characteristics will be described during the baseline period. Certain patient characteristics will be described using all data available prior to the index date (i.e., data prior to December 18, 2019 will also be used if available; see more details in Table 2). Treatment patterns, adherence, and persistence with relugolix, and PSA and testosterone responses (if sample size allows) will be assessed during the follow-up period.

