9.2.1. Inclusion criteria

Patients who met all of the following sample selection criteria will be included:

- Male with ≥ 1 diagnosis of PC (International Classification of Diseases, 10th Revision, Clinical Modification [ICD-10-CM] C61)
- Had ≥ 2 prescriptions of relugolix on or after the first observed PC diagnosis. The initiation date of relugolix will be selected as the **index date**
- At least ≥ 18 years old as of the index date
- Had continuous activity in the data for ≥ 365 days prior to the index date and ≥ 90 days since the index date (unless died within 90 days). The **baseline period** will be defined as the 365-day period prior to the index date. The **follow-up period** will be from the index date to the end of continuous eligibility, data availability, or death, whichever happened first

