Index treatment	
Index treatment regimens include:
 
 • Relugolix monotherapy • Relugolix + NSAA only (at least 90 days of NSAA use) • Relugolix + ARPI +/- NSAA (no chemotherapy) • Relugolix + ARPI + chemotherapy • Relugolix + chemotherapy +/- NSAA (no ARPI) • Relugolix + other (no ARPI, no chemotherapy) 
Index treatment regimen will be defined based on treatments received within 30 days before the index date and within 90 days after the index date.
 
Specific treatments included in each treatment category (i.e., ADT, NSAA, ARPI, chemotherapy, immunotherapy) are described in “Treatment history” in Table 2. Other treatments include immunotherapy, radium 223, olaparib, rucaparib, talazoparib, niraparib and lutetium Lu 177 vipivotide tetraxetan.
 
Number of patients who received any radiotherapy during the index treatment will be summarized.

Variable	Operational definition
Treatment patterns of relugolix	
Treatment patterns of relugolix include:
 
• Continued relugolix as in the index treatment (regardless of discontinuation of concomitant medications)• Continued relugolix with a new add-on systemic PC treatment (excluding ADT)• Discontinued relugolix and switched to another ADT treatment• Discontinued relugolix without switching to another ADT treatment 
Add-on systemic PC treatments include:
 
• ARPI• NSAA• Chemotherapy• Immunotherapy• Radium 223• Ketoconazole• Olaparib• Rucaparib• Talazoparib• Niraparib• Lutetium Lu 177 vipivotide tetraxetan 
Add-on therapy will be evaluated from 90 days after the index period to the end of the follow-up period.

Time to treatment changes	The time to treatment changes of interest include: 
• Time to discontinuation of relugolix• Time to switching to a different ADT treatment• Time to add a new systemic PC treatment to relugolix
Treatment adherence	Adherence to relugolix post the index date will be described using both MPR and PDC: 
• MPR: Sum of the days of supply divided by the number of days between the first fill and the end of the last refill (i.e., including the days of supply from the last refill)• PDC: Sum of the non-overlapping (i.e., not double counting of overlaps) days of supply covered

Variable	Operational definition

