	divided by a pre-determined period following treatment initiation (e.g., 6 and 12 months) Adherence will be described as a continuous variable and as a binary variable (<0.80: non-adherent, ≥ 0.80 : adherent)
Treatment persistence	Persistence to relugolix will be described as the proportion of patients who did not discontinue relugolix (i.e., with a treatment gap, switch to another ADT, or death; the minimum days of treatment gap, e.g., 45 or 60 days, will be finalized based on sample size and clinical input) during the follow-up period. Treatment gaps will be assessed from the end of the days of supply of the previous prescription to the earliest of the next prescription or the end of data availability.
PSA response	Only if sample size is sufficient and among patients with at least one baseline and one follow-up period PSA measure: 
• The number and percentage of patients with $\geq 50\%$ and $\geq 90\%$ decline from the baseline PSA to any PSA measurement during the follow-up period and while on relugolix• The number and percentage of patients with the nadir PSA value during the follow-up period and on treatment of relugolix < 0.01, 0.1, and 0.2 ng/mL
Testosterone response	Only if sample size is sufficient and among patients with at least one follow-up period testosterone measure: 
• The number and percentage of patients with at least one testosterone value of <50ng/dL and <20 ng/dL during the follow-up period and while on relugolix 
If sample size is sufficient, the analysis above may be conducted among patients with at least one baseline and one follow-up period testosterone measure

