9.7.2.3. Time to treatment changes

Kaplan-Meier analysis will be conducted to describe the following time-to-event outcomes for the treatment patterns as listed in [Table 3](#):

PFIZER CONFIDENTIAL

- Time to discontinuation of relugolix
- Time to switching to a different ADT treatment
- Time to add a new systemic PC treatment to relugolix

The number and proportion of patients with the corresponding event will be plotted over time and the number at risk table over time will be presented. The median time to event will be calculated.

9.7.3. Data analysis for Objective 3: To estimate adherence and persistence with relugolix among patients with PC who initiated relugolix

Adherence to relugolix as defined in [Table 3](#) will be described. MPR will be summarized over the entire exposure to relugolix during the follow-up period. PDC will be summarized within the 6, 12, and 18 months (tentatively, pending on the final length of follow-up) since the index date. Means, standard deviations, medians, and interquartile range will be estimated for adherence as a continuous variable. Counts and percentages will be estimated for adherence as a binary variable. Patients will be required to have complete follow-up data during the time to be included in each adherence calculation.

Persistence to relugolix as defined in [Table 3](#) will be described using Kaplan-Meier analysis since the index date. The number and proportion of patients persistent to relugolix will be plotted over time and the number at risk table over time will be presented.

9.7.4. Data analysis for Objective 4: To assess testosterone suppression and PSA responses among ADT naïve patients with PC who initiated relugolix

If sample size is sufficient, the count and percentage of patients with testosterone responses as defined in [Table 3](#) will be calculated among ADT naïve patients with at least one testosterone measure during the follow-up period. Similarly, if sample size is sufficient, the count and percentage of patients with PSA responses as defined in [Table 3](#) will be calculated among ADT naïve patients with at least one baseline and one follow-up period PSA measure.

9.7.5. Data analysis for Objective 5: To describe and compare demographics and clinical characteristics between Black and non-Hispanic White patients with PC who initiated relugolix

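### The add-on window runs past the end of relugolix, and no event or censoring rule reconciles it with an endpoint defined as adding a treatment to relugolix

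*Combined protocol and SAP*

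**What the plan says.** Section 9.3, Table 3, gives the timing rule for add-on treatment: "Add-on therapy will be evaluated from 90 days after the index period to the end of the follow-up period". Section 9.1 fixes when follow-up ends: "The follow-up period will be from the index date to the earliest of death, end of continuous eligibility or end of data availability". Section 9.2.1 agrees. Neither stopping relugolix nor moving to another ADT ends it.

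The same row of Table 3 defines the add-on pattern as "Continued relugolix with a new add-on systemic PC treatment (excluding ADT") and gives men who stop relugolix two patterns of their own, one of them "Discontinued relugolix without switching to another ADT treatment". The matching time-to-event endpoint is "Time to add a new systemic PC treatment to relugolix".

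Section 9.7.2.3 says "Kaplan-Meier analysis will be conducted to describe the following time-to-event outcomes for the treatment patterns as listed in" Table 3. Section 9.7.6 compares these times between Black and non-Hispanic White patients by Cox regression. Neither section says what happens to a man's add-on time when he stops relugolix, switches ADT or dies.

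Elsewhere Table 3 does state an on-drug limit: PSA and testosterone responses are assessed "during the follow-up period and while on relugolix".

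**The concern.** The window includes time off relugolix, while the pattern and endpoint names refer to time on it. A Kaplan-Meier or Cox analysis needs a dated event rule and a censoring rule, and the plan supplies neither at discontinuation.

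Take a man who stops relugolix at month 6, moves to leuprolide and starts an ARPI at month 18. The ARPI start lies inside the stated window, but nothing was added to relugolix. Two competent programmers could treat him differently:

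- **Reading A:** every new systemic agent up to the end of follow-up is an event. He has an event at month 18.
- **Reading B:** only starts on relugolix are events, but the window still runs to the end of follow-up. He stays at risk after month 6 for an event he cannot have while off the drug.

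Reading A mixes intensification on relugolix with later-line treatment. Reading B makes the group that stops sooner look less likely to intensify. In both, the race hazard ratio can pick up a difference in persistence, which Objective 7 already studies in its own right.

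**Working it through.** The documents give no add-on rate, persistence or event count, so there is no figure to reproduce. The check shows how far the readings can diverge.

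**Inputs from the documents**
- The longest possible follow-up is 18 December 2020 to 31 December 2023, or 1,108 days.
- The shortest is 90 days, apart from early deaths.
- Evaluation is taken as starting at day 90 after index. The plan's term for the starting point is undefined, and this point does not turn on it.

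**Assumptions**
- Index dates are uniform, so time at risk after day 90 is uniform from 0 to 1,108 − 90 = 1,018 days, which gives L = 1,018/365 = 2.789 years.
- The new-agent hazard on relugolix is a = 0.10 per year. Off relugolix it is r × a, with r = 0.5, 1 or 2.
- Discontinuation is exponential with 12-month persistence p, so h = −ln(p) per year.
- Deaths and restarts of relugolix are ignored.

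**1. Share of Reading A events that start off relugolix (r = 1)**

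All events per man = 1 − (1 − e^(−aL))/(aL). With aL = 0.2789 this is 1 − 0.2434/0.2789 = 0.127.

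On-relugolix events per man = p^(90/365) × a/(a+h) × [1 − (1 − e^(−(a+h)L))/((a+h)L)].

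| p | h | on-relugolix events per man | off-relugolix share |
|---|---|---|---|
| 0.80 | 0.223 | 0.946 × 0.309 × 0.341 = 0.100 | 1 − 0.100/0.127 ≈ 22% |
| 0.65 | 0.431 | 0.899 × 0.188 × 0.478 = 0.081 | ≈ 36% |
| 0.50 | 0.693 | 0.843 × 0.126 × 0.597 = 0.063 | ≈ 50% |

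A simulation of 400,000 men per setting agrees to within a point. With r from 0.5 to 2 it gives about 12% (p = 0.80, r = 0.5) to 65% (p = 0.50, r = 2).

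A separate calculation used a 20% yearly start rate, 20% to 60% stopping by 12 months, and r = 1 or 2. It gave 13% to 57% with 365 days of follow-up and 21% to 71% with 730 days.

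**2. Effect on the hazard ratio**

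Two groups have the same on-relugolix add-on hazard, so the true ratio is 1.00. Their 12-month persistence is 70% and 50%, and ratios are lower-persistence over higher-persistence group. To a close approximation, at 12 months:

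- Reading A: a group's hazard is a × [p + r(1 − p)].
  - r = 0.5: (0.50 + 0.25)/(0.70 + 0.15) = 0.75/0.85 = 0.88
  - r = 1: 1.00/1.00 = 1.00
  - r = 2: (0.50 + 1.00)/(0.70 + 0.60) = 1.50/1.30 = 1.15
- Reading B: a group's hazard is a × p, so the ratio is 0.50/0.70 = 0.71.
- Censoring at discontinuation: the hazard is a in both groups, so the ratio is 1.00.

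Cox fits to simulated data (1,000,000 men per group, standard error of each log hazard ratio about 0.005 or less) average this over follow-up:

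| Rule | r = 0.5 | r = 1 | r = 2 |
|---|---|---|---|
| Reading A | 0.88 | 1.00 | 1.14 |
| Reading B | 0.71 | 0.72 | 0.72 |
| Censor at discontinuation | 0.99 | 1.00 | 1.00 |

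For Reading A, a 15-point persistence gap gives about 0.92 to 1.12. A 30-point gap (80% versus 50%) gives about 0.84 to 1.23.

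**The case against.** The best defence is that the names already carry the condition. The pattern says relugolix continues, the endpoint says the treatment is added to relugolix, and Section 9.7.2.3 ties the Kaplan-Meier outcomes to those patterns. The window sentence only says where to look. PSA and testosterone need an explicit on-drug phrase because a laboratory value has no built-in link to relugolix, so the contrast with those rows is weak evidence.

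Much of this stands. A reader might infer that the plan sets no on-relugolix condition at all and defines later drugs as add-ons. The wording does not support that. In the four-pattern table and Sankey diagram, a man who stopped relugolix and then started an ARPI belongs in a discontinuation pattern.

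The defence does not settle the time-to-event analysis. If the names exclude later drugs but the window still runs to the end of follow-up, the result is Reading B, which distorts the hazard ratio more in this example. Nor can final pattern membership decide the event. A man who adds an ARPI at month 8 and stops relugolix at month 14 has also discontinued, and a true add-on could be lost.

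A reader might also infer that unequal time off drug is enough to bias the hazard ratio if post-relugolix starts are counted. It is not: with equal start rates on and off drug the ratio stays at 1.00.

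**Conclusion.** The point holds as a mismatch between the stated window and the pattern and endpoint definitions, with no rule to resolve it. It is not a definition that counts post-relugolix drugs as add-ons. If they were counted, they could make up about 12% to 65% of events. With 70% versus 50% persistence, the race hazard ratio could be about 0.88 to 1.14 under Reading A and about 0.72 under Reading B when the true ratio is 1.00. The Reading A distortion needs different start rates on and off drug; the Reading B distortion needs only different persistence.

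All rates are assumed, and nothing in the documents says which race group, if either, stops sooner. The figures show what the text permits, not an expected error. The affected outputs belong to exploratory Objectives 2 and 6, and the primary objective is untouched. The sponsor should settle this before programming.

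**What to change.** - **Window and event.** In Table 3, end the add-on window at the earliest of relugolix discontinuation (as defined in the treatment persistence row, once the gap length is finalised), switch to another ADT, or end of follow-up. Require the new agent to start before that date. The start of the window needs no change for this purpose.
- **Cox model (9.7.6).** Censor at discontinuation or switch, and describe the result as a cause-specific hazard ratio among men still on relugolix, to be read beside the discontinuation result.
- **Descriptive curve (9.7.2.3).** Report cumulative incidence of add-on, with discontinuation or switch and death as competing events.
- **Later therapy.** Report systemic treatment started after relugolix ended in a separate row.
- **Consistency.** Use one add-on event rule for the add-on pattern, the curve and the race comparison.

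The cost is a few sentences in Table 3 and Sections 9.7.2.3 and 9.7.6, one date comparison in the programs, and a competing-risks curve. The downside is fewer add-on events than under Reading A. At 65% persistence and equal rates, about 8.1% of men rather than 12.7% would have one.

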9.9. Limitations of the research methods

The analyses conducted as part of this study are subject to the following limitations, which will be addressed in any write-up of the study:

- As this study will be conducted among veterans, its findings may not be generalizable to other populations
- Certain assumptions will be made in order to depict treatment patterns. However, the definition of treatment patterns will nevertheless be subject to assumptions that may not match up to the prescribing physicians' intent
- Data are subject to inaccuracies in coding of diagnoses. The presence of a diagnosis code in the data does not necessarily mean the presence of disease. The disease may be incorrectly coded, or the code was included as a rule-out criterion
- The presence of a prescription does not necessarily mean the medication was consumed as prescribed. In addition, prescriptions filled over the counter or provided as samples by the physician are not included in the data

- The fact that our entry criteria is at least 2 subscriptions of relugolix means we are selecting patients who were able to tolerate the first month and followed up to receive a second month. How this cohort relates to all patients given relugolix is unknown.

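### Persistence and fixed-window PDC cannot separate a completed limited course from other stopping, so pooled results, and the race comparison if course mix differs by race, can reflect case mix

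*Combined protocol and SAP*

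**What the plan says.** **Persistence.** Table 3 in Section 9.3 has "Persistence to relugolix will be described as the proportion of patients who did not discontinue relugolix", and explains discontinuation as "with a treatment gap, switch to another ADT, or death". A gap must reach a minimum length before it counts: "the minimum days of treatment gap, e.g., 45 or 60 days" are the examples, to be settled later on sample size and clinical input. Of the four treatment patterns in the same table, two describe stopping, with and without a switch to another ADT. Neither is divided by reason.

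**Adherence.** Two measures are planned. The days covered in PDC are "divided by a pre-determined period following treatment initiation (e.g., 6 and 12 months". Section 9.7.3 adds a third window: "PDC will be summarized within the 6, 12, and 18 months (tentatively, pending on the final length of follow-up) since the index date". It requires complete follow-up through the window, but not that the man is still on treatment. MPR instead uses the time from first fill to the end of the last refill. Both are cut at 0.80.

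**Variables that could separate the men.** Section 9.2.1 admits any prostate cancer diagnosis. Table 2 derives metastatic status and lists radiotherapy in the baseline year. Table 3 adds: "Number of patients who received any radiotherapy during the index treatment will be summarized". Metastatic status is used in Section 9.7.1 to compare baseline characteristics. Sections 9.7.2.3, 9.7.3, 9.7.6 and 9.7.7 name neither variable.

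**Race comparison.** Sections 9.7.6 and 9.7.7 plan unadjusted and adjusted models. The covariates will be chosen from the Section 9.7.5 results and clinical input.

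**Limitation.** Section 9.9 says that treatment patterns are "subject to assumptions that may not match up to the prescribing" physician's intent. It adds no analysis.

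**The concern.** Persistence and adherence will be read as how well men stay on relugolix. A man whose course was always meant to end, and who took every dose, stops refilling, passes the gap threshold, and is counted as discontinued without switching. If his course was short relative to the window, PDC also labels him non-adherent.

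If such men exist in the cohort, the pooled figures for Objective 3 fall as their share rises, with no change in behaviour. If their share or course length differs between Black and non-Hispanic White men, the Objective 6 and 7 comparisons can show a difference in discontinuation, persistence or PDC where none exists, or hide a real one.

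**Working it through.** The plan gives no persistence, adherence or sample-size figure, so there is nothing to reproduce. From the documents come the event definition, the PDC windows of 6, 12 and 18 months, the 0.80 cut-off and the MPR denominator. **Assumed**, because the documents give no values: the share *f* of men on a limited course, its length *L*, and the unplanned stopping hazard *h*. The lengths below are arithmetic examples, not proposals.

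**1. PDC of a fully taken course.** PDC = min(*L*/*W*, 1) for window *W*. It falls below 0.80 when *L* < 0.80 × *W*: 0.80 × 6 = 4.8 months, 0.80 × 12 = 9.6 months, 0.80 × 18 = 14.4 months.

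| Course (months) | PDC at 6 | PDC at 12 | PDC at 18 | MPR |
|---|---|---|---|---|
| 4 | 0.67 | 0.33 | 0.22 | 1.00 |
| 6 | 1.00 | 0.50 | 0.33 | 1.00 |
| 9 | 1.00 | 0.75 | 0.50 | 1.00 |
| 12 | 1.00 | 1.00 | 0.67 | 1.00 |
| 18 or 24 | 1.00 | 1.00 | 1.00 | 1.00 |

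**2. Pooled persistence at 12 months.** If a share *f* has a 6-month course, reported persistence = (1 − *f*) × exp(−12*h*). Without limited courses, *h* = 0.02 per month gives exp(−0.24) = 0.79, and *h* = 0.04 gives exp(−0.48) = 0.62.

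| Share *f* | *h* = 0.02 | *h* = 0.04 |
|---|---|---|
| 0 | 79% | 62% |
| 10% | 71% | 56% |
| 20% | 63% | 50% |
| 40% | 47% | 37% |

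**3. Race hazard ratio (Black vs non-Hispanic White).** Simulated Cox model with the same unplanned hazard in both groups (0.02 or 0.04 per month), planned stops at about 6 months, and uniform censoring from 3 to 36 months. The true ratio is 1. The ranges cover both hazards and repeated runs.

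| Limited-course share, White vs Black | Unadjusted HR |
|---|---|
| equal | 1.00 |
| 20% vs 30% | 1.13-1.23 |
| 15% vs 30% | 1.22-1.38 |
| 30% vs 20% | 0.82-0.87 |

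With unplanned stopping of 15-35% a year, and courses of either 6 months or a mix of 4 to 24 months, the ranges widen to 1.11-1.27 (20% vs 30%) and 0.78-0.91 (30% vs 20%).

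**4. What stratifying achieves.** Stratifying on *true* course status returns 0.99-1.01. The data do not record true status. With a proxy of assumed 80% sensitivity and 90% specificity, unadjusted ratios of 1.13-1.34 fall only to about 1.09-1.22.

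**The case against.** The strongest reply is that the premise is not in the documents. They nowhere say that a man receives a limited relugolix course, how long it would last, or that it differs by race. That stands: every size above is conditional. The supporting signs are indirect, namely an all-stage cohort, radiotherapy captured at baseline and during index treatment, and testosterone recovery listed in Section 7 as a potential benefit.

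Second, the plan reports MPR beside PDC. This also stands. A reader might infer that completed courses are scored as non-adherent generally, but MPR ends with the last refill and is 1.00 for a fully taken course of any length. Nor does every short gap count as stopping, since a minimum applies.

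Third, the adjusted models may deal with the race question. Metastatic status and baseline radiotherapy are Table 2 variables, so Section 9.7.5 will compare them by race, and clinical input can add others. This stands in part. Adjustment is possible but not promised. Radiotherapy during index treatment appears only in Table 3, so the Section 9.7.5 comparison would not bring it up. The unadjusted ratio is reported in any case.

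Fourth, these objectives are exploratory, the study tests no stated hypothesis, and time on drug is descriptive whatever the reason for stopping. This limits the weight of the point. It does not help a reader who sees a low 0.80-threshold adherence rate or a race hazard ratio without knowing that course mix may drive it.

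**Conclusion.** The point holds in a conditional form. On the written definitions, completion and other discontinuation cannot be told apart, and fixed-window PDC marks fully taken courses below 4.8, 9.6 or 14.4 months as non-adherent. Those statements need no assumption about prevalence.

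The effect on the results does need one. With 10-40% of men on a 6-month course and 2-4% monthly unplanned stopping, 12-month persistence of 62-79% would be reported as 37-71%.

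A reader might infer that the race hazard ratio is therefore biased, or is biased against Black men. The documents do not support that. With equal shares and lengths the ratio stays at 1.00. With shares of 20% and 30% the unadjusted ratio is about 1.13-1.23 in one direction and 0.8-0.9 in the other, and the adjusted models may reduce it. Confidence is medium. The change should be made because it is cheap and bears on Objectives 2, 3, 6 and 7.

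**What to change.** - **Sections 9.7.2.3, 9.7.3, 9.7.6 and 9.7.7:** keep the overall results. Also report time to discontinuation, persistence and PDC for (a) metastatic men, (b) non-metastatic men with radiotherapy in the baseline or index window, and (c) non-metastatic men without it.
- **Adjusted race models:** pre-specify these three groups as strata or covariates in the Cox models and as covariates in the adherence GLMs, whatever Section 9.7.5 shows.
- **Wording:** do not relabel stops in group (b) as planned, because that would hide unplanned stops among men given radiotherapy. State that discontinuation there may include completed courses, and present PDC beside MPR.
- **Section 9.9:** state that intent is not recorded and that the groups are an imperfect proxy, so the bias is reduced and not removed.

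**Cost:** plan wording, extra tables and smaller cells. The annex has no code list for radiotherapy or for metastasis, so both must be added; the plan's existing variables already need them. The groups use information from up to 90 days after the index date, as the plan's own metastatic and index-regimen definitions do. No new data source is needed, and no clinical rule changes.

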The same descriptive analysis described in [Section 9.7.1](#) will be conducted in Black and non-Hispanic White patients separately. If the sample sizes allow, SMD will be calculated to compare the patient baseline characteristics between Black vs. non-Hispanic White cohorts. Additionally, p-values from appropriate statistical tests (e.g., t-tests or rank-sum tests for continuous variables and chi-square tests for categorical variables) comparing Black vs. non-Hispanic White cohorts will be reported.

9.7.6. Data analysis for Objective 6: To describe and compare time to treatment changes between Black and non-Hispanic White patients with PC who initiated relugolix

The same descriptive analyses described in Section 9.7.2.3 will be conducted in Black and non-Hispanic White patients separately. Unadjusted and adjusted comparisons between the two race groups will be conducted. Cox proportional hazards (PH) regressions will be used to compare the time to treatment changes between the two race groups. Patient characteristics to be included in the adjusted models will be selected based on findings in Section 9.7.5 and clinical input.

9.7.7. Data analysis for Objective 7: To estimate and compare adherence and persistence with relugolix between Black and non-Hispanic White patients with PC who initiated relugolix

The same descriptive analyses described in Section 9.7.3 will be conducted in Black and non-Hispanic White patients separately. Unadjusted and adjusted comparisons between the two race groups will be conducted. Generalized linear models will be used to compare adherence to relugolix between the two race groups. Cox PH regressions will be used to compare persistence between the two race groups. Patient characteristics to be included in the adjusted models will be selected based on findings in Section 9.7.5 and clinical input.

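### Persistence counts death as discontinuing relugolix, and no planned analysis is clearly specified to show overall stopping apart from death

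*Combined protocol and SAP*

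**What the plan says.** The persistence row of Table 3 (Section 9.3) spells out discontinuing relugolix as "with a treatment gap, switch to another ADT, or death". The gap length is still open: "the minimum days of treatment gap, e.g., 45 or 60 days, will be finalized based on sample size and clinical input". A gap runs from the end of the previous supply to the next prescription or the end of the data, whichever is earlier; death is not named as an end point for it.

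Section 9.7.3 applies that definition to a Kaplan-Meier analysis from the index date: "The number and proportion of patients persistent to relugolix will be plotted over time". Section 9.7.7 carries it into the race comparison: "Cox PH regressions will be used to compare persistence between the two race groups", unadjusted and adjusted.

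Section 9.7.2.3 lists further Kaplan-Meier outcomes, among them "Time to discontinuation of relugolix" and "Time to switching to a different ADT treatment". Section 9.7.6 compares these by race: "Cox proportional hazards (PH) regressions will be used to compare the time to treatment changes between the two race groups". Neither section, nor the matching row of Table 3, says what counts as discontinuation or how death is handled. Table 3 also has a treatment-pattern category "Discontinued relugolix without switching to another ADT treatment", without saying where a death on treatment belongs.

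Sections 9.1 and 9.2.1 end follow-up at death, and Section 9.4 states that date of death is held.

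**The concern.** Objectives 3, 6 and 7 ask how the drug is used. Under the Table 3 definition, a man who refills on time until he dies has the same outcome as a man who gives the drug up. The persistence curve then falls with deaths as well as with stopping. A mortality difference between Black and non-Hispanic White patients would appear as a persistence difference even if the two groups stopped at exactly the same rate. It could equally mask a real difference in stopping.

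A composite that includes death is a legitimate outcome if a companion analysis shows its treatment-use part. Time to discontinuation looks like that companion, but the plan does not define it, and the only definition available to borrow includes death.

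**Working it through.** **Step 1: what each analysis isolates.**

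- Persistence (9.7.3, 9.7.7): gap, switch or death, as stated.
- Time to discontinuation (9.7.2.3, 9.7.6): not stated. If it takes the Table 3 wording, it has the same event as persistence and repeats it. If it takes the follow-up rule, death censors. Both readings are open.
- Time to switching: death is not part of the named event, but men who stop without starting another ADT are not events either. It cannot stand in for overall stopping.
- Gap rule: because a gap may run to the end of the data, a man who dies on treatment could still be scored as having a gap after his last supply, even if death were removed from the event list. The follow-up limit would have to be applied to prevent this.

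**Step 2: formulas.** The plan states no stopping rate, death rate, event count or sample size, so there is no figure to reproduce. Everything below is assumed, with constant hazards. Let s be the monthly hazard of gap or switch, d the monthly hazard of death in the reference group, and HRd the mortality hazard ratio. Stopping is identical in the two race groups.

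- 12-month composite persistence = exp(−12 × (s + d))
- 12-month persistence with deaths censored = exp(−12 × s)
- Composite hazard ratio = (s + d × HRd) / (s + d)

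The last line is a weighted average of the stopping hazard ratio (here 1.0) and the mortality hazard ratio, with weight d / (s + d) on mortality. It equals the stopping hazard ratio only if there are no deaths or the two ratios agree.

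**Step 3: numbers, with s = 0.03.** With deaths censored, 12-month persistence is exp(−0.36) = 69.8%.

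| d per month | Composite persistence at 12 months | Composite HR, HRd = 1.5 | Composite HR, HRd = 0.7 |
|---|---|---|---|
| 0.004 | exp(−0.408) = 66.5% | 0.0360 / 0.034 = 1.06 | 0.0328 / 0.034 = 0.96 |
| 0.008 | exp(−0.456) = 63.4% | 0.0420 / 0.038 = 1.11 | 0.0356 / 0.038 = 0.94 |
| 0.012 | exp(−0.504) = 60.4% | 0.0480 / 0.042 = 1.14 | 0.0384 / 0.042 = 0.91 |

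The composite is 3.3 to 9.4 percentage points below the death-censored figure. The hazard ratio moves away from 1.0 in either direction although stopping is the same.

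**Step 4: dependence on the stopping rate.** With s = 0.05 and HRd = 1.5, the composite hazard ratio is 0.056 / 0.054 = 1.04 at d = 0.004 and 0.068 / 0.062 = 1.10 at d = 0.012. More frequent stopping dilutes the effect.

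**Step 5: Kaplan-Meier against cumulative incidence.** Take a 12-month stopping risk of 40% with deaths censored and a death risk of 5% with stopping censored. Composite persistence is 0.60 × 0.95 = 57.0%. With deaths censored it is 60.0%. With death as a competing event, the share of the total hazard due to stopping is 0.511 / (0.511 + 0.051) = 0.909, the cumulative incidence of stopping is 0.909 × 43.0% = 39.1%, and its complement is 60.9%. In this example, whether death counts as an event matters more than the choice between the last two.

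**The case against.** The strongest reply is that the composite is openly stated and the separate analysis may already be there. Time to discontinuation and time to switching are listed as outcomes in their own right, overall and by race, and follow-up ends at death. If time to discontinuation censors at death, its planned Cox model by race is already a cause-specific model, and only the descriptive curve would differ (60.0% against 60.9% in the example above). The objectives affected are exploratory, no hypotheses are specified, and adjustment for patient characteristics could narrow a mortality difference. The illustration also depends on an assumed stopping rate.

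Most of this stands, and it limits the point. A reader might infer that no planned analysis shows stopping at all, or that time to discontinuation necessarily reproduces the persistence curve. The documents do not support either: switching is analysed separately, and the follow-up rule leaves room for censoring at death. A reader might also infer that removing deaths from the PDC calculation makes adherence and persistence describe different populations. That goes too far. MPR covers the whole exposure rather than a fixed window, so the completeness requirement does not clearly remove deaths from it. For PDC the requirement also drops patients with short administrative follow-up, so the populations differ whatever is done about death.

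The reply does not settle which reading of time to discontinuation applies. Two analysts could follow this plan and report different results, and the reading closest to the written definition counts death.

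**Conclusion.** The point holds as one of specification and interpretation. Persistence, and its hazard ratio by race, mix stopping with mortality by definition. The plan does not say whether death is an event, a censoring point or a competing event for time to discontinuation, so no planned analysis is clearly specified to show overall stopping apart from death.

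The actual size and direction cannot be determined from the documents. The range of 1.06 to 1.14 rests on constant hazards, identical stopping by race, a mortality hazard ratio of 1.5 and the assumed monthly rates. A mortality hazard ratio below 1 would push the result the other way. Nothing in the documents indicates that mortality differs by race in this cohort. The primary objective, a baseline description, is unaffected. The change is worth making because it is cheap and the race comparison of drug use is otherwise hard to interpret.

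**What to change.** 1. Keep the composite for persistence in Table 3 and 9.7.3, labelled as including death.
2. In Table 3, 9.7.2.3 and 9.7.6, define time to discontinuation as gap or switch only, with death as a competing event: cumulative incidence for description, and cause-specific Cox regression, censoring at death, for the comparison by race.
3. State that gap assessment ends at death, so that time after death cannot be scored as a gap.
4. In 9.7.7, report the cause-specific hazard ratio beside the composite one, with the number of deaths on relugolix in each race group.

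The cost is a few sentences in these sections and a small amount of extra analysis. No new data are needed, because date of death is already in the data source. Persistence and time to discontinuation would then answer two distinct questions.
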